5.6.3. Laboratory assays

Please refer to [APPENDIX A](#) for a detailed description of the assays performed in the study and to [APPENDIX B](#) for the address of the clinical laboratories used for sample analysis.

Table 6 Humoral Immunity (Antibody determination) (amended 19 February 2015)

System	Component	Method	Kit / Manufacturer	Unit	Cut-off	Number of subject	Laboratory ⁽³⁾
Serum ⁽¹⁾	Anti-CMV tegument protein IgG	ELISA	Biotest like assay	EU/mL	TBD	All subjects	TBD
Serum ⁽¹⁾	Anti-gB IgG	ELISA	In house	EU/mL	54	Subset ⁽²⁾	TBD
Serum ⁽¹⁾	Anti-CMV tegument protein avidity index	ELISA	Biotest like assay	NA	NA	Subset ⁽²⁾	TBD
Serum ⁽¹⁾	Anti-gB IgG avidity index	ELISA	In house	NA	NA	Subset ⁽²⁾	TBD
Serum ⁽¹⁾	Anti-CMV IgM	ELISA	Diasorin or equivalent	NA	NA	Subset ⁽²⁾	TBD
Serum	Anti-CMV neutralizing antibodies (multiple cell lines) and /or other virus strains	Seroneutralisation	In house	ED ₅₀	TBD	Subset ⁽²⁾	TBD
Serum ⁽¹⁾	Antibody recognition profile	Peptide microarray	TBD	NA	NA	Subset ⁽²⁾	TBD

Note: Most of the read-outs described in this table might be done if deemed necessary.

⁽¹⁾ Coating Ag will be defined based on available commercial kits or in house developed assays (such as whole virus proteins or tegument proteins or others to be defined).

⁽²⁾ Subset will be defined based on the outcome of primary/secondary endpoints or the development of the assay. The subset is the minimum number of subjects that will be tested. If applicable, all subjects could be tested.

⁽³⁾ Refer to [APPENDIX B](#) for the laboratory addresses.

TBD = To be determined, gB = glycoprotein B; Ig = immunoglobulin, ELISA = Enzyme-linked immunosorbant assay, EU = ELISA unit, NA = not applicable; ED₅₀ = effective dose 50, Ag = antigen.

The laboratories that will perform antibody determination are not yet identified and will be defined as soon as available.

Table 7 Molecular Biology (amended 19 February 2015)

System	Test	Component	Method	Unit	Number of subject	Laboratory ⁽⁴⁾
Urine	Viral load detection	CMV DNA	quantitative PCR	Copy/mL	All subjects ⁽¹⁾	DDL
Urine	Viral load detection	CMV DNA	quantitative PCR	Copy/mL	All Newborns	BARC
Saliva	Viral load detection	CMV DNA	quantitative PCR	Copy/mL	Subset ⁽³⁾	DDL
Saliva	Viral load detection	CMV DNA	quantitative PCR	Copy/mL	All Newborns	BARC
Plasma/buffy coat	Viral load detection	CMV DNA	quantitative PCR	Copy/mL	Subset ⁽³⁾	DDL
TBD ⁽²⁾	Multi strain typing	CMV DNA	CMV strain typing	NA	Subset ⁽³⁾	TBD
Whole blood	RNA transcript	TBD	mRNA microarray or qPCR	NA	Subset ⁽³⁾	TBD

Note: Most of the read-outs described in this table might be done if deemed necessary.

⁽¹⁾ In seronegative subjects, testing of viral load will only be done upon seroconversion.

⁽²⁾ The matrix will be determined based on the results obtained with the PCR and the availability of the assay.

⁽³⁾ Subset will be defined based on the outcome of primary/secondary endpoints or the development of the assay.

The subset is the minimum number of subjects that will be tested. If applicable, all subjects could be tested.

⁽⁴⁾ Refer to [APPENDIX B](#) for the laboratory addresses.

TBD = To be determined, mRNA = messenger Ribonucleic acid; PCR = Polymerase Chain reaction; DNA = deoxyribonucleic acid; NA = not applicable.

In case the results from a 4-month Site Visit suggests primary or secondary (re-infection/re-activation) infection, testing related to the tertiary endpoints will be done on selected samples collected during the Sample Collection Visit. The selection of samples to be tested will be based on the qPCR results obtained following the Site visits.

If the results from a 4-month Site Visit suggest no primary or secondary (re-infection/re-activation) infection, the samples collected during the Sample Collection Visit period will be stored and used if applicable (e.g. negative control for laboratory validation).

Collected samples will be used for purposes related to the quality assurance of data generated within the scope of this protocol, such as for maintenance of assays described in this protocol and comparison between analytical methods and/or laboratories.

The laboratories that will perform antibody recognition profile, multi strain typing and RNA transcript assays are not yet identified and will be defined as soon as available.

5.6.4. Biological samples evaluation

5.6.4.1. Read-outs

Table 8 Read-outs (amended 19 February 2015)

Sampling time point		Subset Name	No. subjects	Component
Type of contact and time point	Sampling time point			
Site visits: (V1 to V10)	Months 0, 4, 8, 12, 16, 20, 24, 28, 32, and 36	All subjects	All	Anti-CMV tegument protein IgG (serum)
		Subset ⁽²⁾	TBD	Anti-gB IgG (serum)
		All subjects ⁽¹⁾	TBD	CMV DNA (urine)
		Subset ⁽²⁾	TBD	Anti-CMV tegument protein IgG antibody avidity index
				Anti-gB IgG antibody avidity index
		Subset ⁽²⁾	TBD	CMV DNA (saliva, blood)
		Subset ⁽²⁾	TBD	Anti-CMV IgM (serum)
		Subset ⁽²⁾	TBD	Anti-CMV neutralizing antibodies (multiple cell lines and/or other viral strains)
		Subset ⁽²⁾	TBD	Antibody recognition profile
		Subset ⁽²⁾	TBD	Multi strain typing
Site visit (V1 and V4*)	Months 0 and 12*	Subset ⁽²⁾	TBD	RNA transcript
Sample Collection Visits (SCV 1 to SCV 9)	Month 2, 6, 10, 14, 18, 22, 26, 30, 34 ⁽³⁾	Subset ⁽²⁾	TBD	CMV DNA (urine + saliva)
	Upon delivery	Newborn	TBD	CMV DNA urine and/or saliva

⁽¹⁾ In seronegative subjects, testing of viral load will only be done upon seroconversion.

⁽²⁾ Subset will be defined based on the outcome of primary/secondary endpoints or the development of the assay.

The subset is the minimum number of subjects that will be tested. If applicable, all subjects could be tested.

⁽³⁾ Testing will be done on selected samples only if the samples at the following 4-month Site Visit time-point is positive. If the 4-month sample is negative for CMV infection/re-infection, the samples self-collected during the inter-visit period will be stored and be used if applicable. The selection of samples to be tested will be based on the qPCR results obtained following the Site visits.

* **Blood sample will be collected until approval of protocol amendment 2.**

DNA = deoxyribonucleic acid; RNA = Ribonucleic acid

IgG = immunoglobulin G; IgM = immunoglobulin M; gB = glycoprotein B; TBD = To be determined.

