8. DATA EVALUATION: CRITERIA FOR EVALUATION OF OBJECTIVES

8.1. Endpoints

8.1.1. Primary endpoints

- Occurrence of CMV secondary infections determined in all seropositive subjects on samples collected during the 4-month Site Visits until study conclusion:
 - *Anti-CMV tegument protein IgG antibody concentration in serum (ELISA).*
 - *Number of CMV DNA copies (pp65 or other genes) in urine (qPCR).*

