8.1.3. Tertiary endpoints (amended 19 February 2015)

- Further characterization of primary infection in initially seronegative subjects during the 4-month Site Visits until study conclusion (testing done upon seroconversion) **might be done**:
 - *Number of CMV DNA copies (pp65 or other genes) in urine (qPCR).*
- Further characterization of primary and /or secondary CMV infections in a subset of subjects on selected samples of the Sample Collection Visits* **might be done**.
 - *Number of CMV DNA copies (pp65 or other genes) in urine (qPCR).*
 - *Number of CMV DNA copies (pp65 or other genes) in saliva (qPCR).*

* *In case of a positive sample at a 4-month Site Visit time point, testing-might be done on selected samples collected during the Sample Collection Visit.* The selection of samples to be tested will be based on the qPCR results obtained following the Site visits.

- Further characterization of primary and /or secondary CMV infections in a subset of subjects on all available samples of the 4-month Site Visits **might be done**:
 - *Anti-CMV tegument protein IgG antibody avidity index in serum (ELISA).*
 - *Anti-gB IgG antibody concentration in serum (ELISA).*
 - *Anti-gB IgG antibody avidity index in serum (ELISA).*
 - *Anti-CMV IgM antibody concentration in serum (ELISA).*
 - *Number of CMV DNA copies (pp65 or other genes) in saliva and blood (qPCR).*
 - *Assessment of anti-CMV neutralizing antibodies on different target cells and/or other virus strains.*

- Development of assays that will allow differentiating re-infection from re-activation from primary infection in a subset of subjects **might be done**.
 - *Characterization of CMV strains by genotyping/sequencing.*
 - *Exploring the CMV strain specific antibody profile using peptide microarrays.*
- Assessment of the expression of host genes* using techniques such as qPCR or mRNA microarray in a subset of subjects **might be performed**.
 - * excluding genes related to hereditary characteristics of the subject.
- Evaluation of the impact of demographic, social or behavioral factors upon CMV infection **might be performed**.
- Occurrence of congenital CMV infection in newborns of subjects who become pregnant during the study **might be evaluated**:
 - *Evidence of CMV DNA in urine and/or saliva of newborns within 10 days of delivery by using qPCR (pp65 or other genes) might be tested.*

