8.7.4. Tertiary objectives (amended 19 February 2015)

Based on the results of primary and secondary endpoints, following statistical analyses on tertiary endpoints might be done:

Descriptive statistics will be provided for the number of CMV DNA copies in urine at each timepoint for which a sample is available time-points and the percentage of CMV seronegative subjects with presence of CMV DNA in urine will be tabulated (with 95% CI).

For all results of assays performed for the further characterization of primary and/or secondary CMV infections, descriptive statistics will be provided for each assay at each timepoint for which a sample is available time-points.

Analysis performed for the evaluation of the impact of demographic, social or behavioral factors upon CMV infection will be described in a separate document (SAP).

Analysis of results following genotyping/sequencing, mRNA microarray and peptide microarrays will also be described in a separate document (SAP).

The number and percentage of CMV infected newborns will be tabulated and descriptive statistics will be provided for the number of CMV DNA copies.

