5.3. Other Analysis Sets

All subjects in the All Enrolled Set who consent to provide exploratory assay data at relevant time points will be included in an exploratory assay subset. Subgroup analysis sets will be included based on two-fold and four-fold increases in anti-CMV tegument protein IgG antibodies in serum among CMV seropositive subjects. The analyses of the tertiary endpoints will be detailed in a separate statistical analysis plan.

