6.2.3. Analysis of Tertiary objective

Descriptive statistics will be provided for the number of CMV DNA copies in urine at each time point for which a sample is available and the percentage of CMV seronegative subjects with presence of CMV DNA in urine will be tabulated (with 95% CI).

For all results of assays performed for the further characterization of primary and/or secondary CMV infections, descriptive statistics will be provided for each assay at all selected time points for which a sample is available.

The analysis of tertiary objectives will be described in an analysis plan amendment (before unblinding) or in an additional analysis request (after unblinding).

For further details on standard business rule for GMT computation, see annex 1.

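### The characterisation assays are summarised only by time point, with no alignment to the infection event, so in a cases-only subset the Month 4 to Month 32 rows would dilute transient markers

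*Protocol*

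**What the plan says.** Protocol 8.1.3 places avidity, anti-gB, IgM, saliva and blood DNA and neutralising antibodies under "Further characterization of primary and /or secondary CMV infections in a subset of subjects on all available samples of the 4-month Site Visits", as work that might be done.

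Table 8 in Protocol 5.6.4.1 gives the selection rule: "Subset will be defined based on the outcome of primary/secondary endpoints or the development of the assay". It then adds: "The subset is the minimum number of subjects that will be tested. If applicable, all subjects could be tested".

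The selecting outcome has a long window. Protocol 8.1.1 defines the primary endpoint as "Occurrence of CMV secondary infections determined in all seropositive subjects on samples collected during the 4-month Site Visits until study conclusion", and 8.1.2 uses the same window for primary infection in seronegative subjects.

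Two sentences state the summary. Protocol 8.7.4 says that "descriptive statistics will be provided for each assay at each timepoint for which a sample is available time-points". SAP 6.2.3 says that "descriptive statistics will be provided for each assay at all selected time points for which a sample is available", without saying how time points are selected.

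For Sample Collection Visits, Table 8 footnote 3 says: "Testing will be done on selected samples only if the samples at the following 4-month Site Visit time-point is positive".

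The SAP also defers. SAP 5.3 says: "The analyses of the tertiary endpoints will be detailed in a separate statistical analysis plan". SAP 6.2.3 sends the tertiary analysis to a plan amendment before unblinding or to an additional analysis request after it.

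**The concern.** These assays are there to show what happens around a primary or secondary infection. One tertiary objective (Protocol 2.3) is the diagnostic value of the different assays, which requires marker values relative to the event. Study month does not supply that. If the subset consists of cases, the Month 12 row holds subjects infected some months earlier, subjects just found positive, and subjects who will not be infected until Year 3.

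A marker that is raised only briefly, such as IgM, low avidity or DNA in saliva or blood, is then averaged over mostly irrelevant samples. Nor do the Sample Collection Visit rows compare with the Site Visit rows by month: the former hold only subjects whose next Site Visit was positive, the latter the whole subset.

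At stake is the usefulness of the tertiary tables. The primary and secondary incidence estimates are not touched.

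**Working it through.** **Inputs.** Evaluable seropositive subjects: 200. Assumed incidence: 2% per year. Follow-up: 3 years. Expected re-infected subjects: about 12 (all Protocol 8.2). Site Visits: 10, at Months 0, 4, … 36, hence nine between-visit intervals (Protocol 3).

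**The plan's own figure.** 200 × 0.02 × 3 = 12.0. With yearly compounding, 200 × (1 − 0.98³) = 11.8. The stated 12 reproduces.

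**Assumptions for the illustration.** The subset is the 12 cases only; each has one event; events are spread evenly over the nine intervals; no visit is missed. The documents give none of these four.

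**By study month.** Cases newly positive at any follow-up visit: 12/9 = 1.33, or 1/9 = 11.1% of the subset. Share already infected at the k-th follow-up visit: k/9.

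| Month | Already infected, of 12 | Share |
|---|---|---|
| 0 | 0 | 0% |
| 4 | 1.3 | 11% |
| 8 | 2.7 | 22% |
| 12 | 4.0 | 33% |
| 16 | 5.3 | 44% |
| 20 | 6.7 | 56% |
| 24 | 8.0 | 67% |
| 28 | 9.3 | 78% |
| 32 | 10.7 | 89% |
| 36 | 12.0 | 100% |

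Months 4 to 32, eight of the ten Site Visits, hold both pre- and post-event samples. Month 0 is entirely before the on-study event, and by Month 36 every case has had her first event. A constant hazard in place of an even spread moves these shares by less than one percentage point.

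**Aligned to the first positive visit.** The number with a sample j visits after the event is 12 × (9 − j)/9:

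- visit before the event: 12
- event visit: 12
- +4 months: 12 × 8/9 = 10.7
- +8 months: 12 × 7/9 = 9.3
- +12 months: 12 × 6/9 = 8.0

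**Two marker types.** A marker positive in every case, but only at the event visit, shows as 11% at each follow-up month and as 100% at the aligned event visit. A marker that stays positive after infection climbs from 11% at Month 4 to 100% at Month 36. It remains visible by month, although the climb reflects cases accumulating and not the marker's course within a subject.

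**If all 200 seropositive subjects were tested.** Outcome selection disappears, but 1.33/200 = 0.7% would be at their event visit in any follow-up row, so dilution is greater in a table that pools them.

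**The case against.** The strongest reply is that this is a placeholder sentence and not the finished plan. Protocol 8.7.4 says these analyses might be done, the SAP defers the tertiary analysis twice, the table shells are in a document not seen here, and SAP section 7 limits everything to descriptive use. That stands as a limit on how much weight the point can bear. It does not answer it. For these assays Protocol 8.7.4 itself gives the per-time-point summary; it refers out to the SAP only for the demographic and behavioural, genotyping, mRNA and peptide microarray analyses. Neither deferral mentions alignment, and one route runs after unblinding. In a study that Protocol 3 describes as uncontrolled, that is no safeguard against setting the rule once assay results are known.

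A reader might also infer more than the documents support:

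- *That the subset is always picked by infection.* It may instead follow assay development, or be widened to all subjects.
- *That every time point mixes pre- and post-infection samples.* For first events, Months 0 and 36 do not.
- *That these assays cannot characterise infection.* Serial samples and the first positive visit are available, so results can be re-indexed, and Sample Collection Visit testing is already triggered by an event. The shortfall is in the stated tables, not in the data.
- *That 11% applies generally.* It needs one event per subject and a marker positive at a single visit. SAP 6.2.1 expects some subjects to have several events, and the 12 covers neither re-activations counted separately nor primary infections, for which no number is given.
- *That study-month reading is certain in the SAP.* Its wording is selected time points, with no selection rule. The protocol's wording supports a by-visit reading more directly.

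**Conclusion.** The point holds in limited form. The documents allow an outcome-selected subset, test it on samples from before and after the event, and state no summary other than by time point. For a cases-only subset, eight of ten Site Visit rows would be mixed, and a one-visit marker would appear at about 11% per follow-up month instead of 100% at the aligned event visit. Those figures rest on the four illustrative assumptions and should be read as showing the direction and rough scale of dilution for transient markers. Repeat events would blur the before/after split further; persistent markers suffer less. The change is worth making because event-time alignment is plainly better suited to the purpose of these endpoints and costs little, but the consequence is confined to optional, descriptive tertiary results.

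**What to change.** In SAP 6.2.3, or in the deferred tertiary plan, and before assay results are seen:

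1. Define an index event visit for each case (first event). State which event definition in SAP 6.2.1 sets it for seropositive subjects, and how repeat events are handled.
2. Summarise each characterisation assay by time from that visit: last pre-event visit, Sample Collection Visit in the event interval, event visit, then +4, +8 and +12 months, with the number contributing at each.
3. Report paired change from the last pre-event sample, separately for primary and secondary infection.
4. Show the event-triggered Sample Collection Visit results on this scale.

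By-visit tables may be kept alongside. Protocol 8.7.4 should carry a matching sentence if it is next amended.

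Cost: one derived variable, extra tables and the need to agree an index rule for repeat events. No new samples or assays are required. Numbers thin out after the event (about 8 of 12 at +12 months in the illustration), so later windows will be imprecise.

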6. SERIOUS ADVERSE EVENTS

Only SAEs related to study participation will be collected and reported during the entire study period.

The investigator or site staff is/are responsible during the study for the detection and documentation of events meeting the criteria and definition of a SAE as provided in this protocol.

Each subject/subject's parent(s)/LAR(s) will be instructed to contact the investigator immediately should they/the subject manifest any signs or symptoms they perceive as serious.

6.1. Safety definitions

6.1.1. Definition of an adverse event

An adverse event (AE) is any untoward medical occurrence in a subject, temporally associated with the use of a medicinal product, whether or not considered related to the medicinal product, or temporally associated with a study procedure.

For an AE to be reportable, there is a minimum set of criteria (as recommended by the Council for International Organizations of Medical Sciences (CIOMS) and ICH) to be considered:

- an identifiable reporter
- an identifiable patient,
- suspect medicinal product (immunization history)
- detailed description of the event
- suspected causal relationship (event is explicitly labelled as "related" by the reporter)

An AE can therefore be any unfavourable and unintended sign (including an abnormal laboratory finding), symptom, or disease (new or exacerbated) temporally associated with the use of a medicinal product. For marketed medicinal products, this also includes failure to produce expected benefits (i.e. lack of efficacy), abuse or misuse.

Examples of an AE include:

- Significant or unexpected worsening or exacerbation of the condition/indication under study.
- Exacerbation of a chronic or intermittent pre-existing condition including either an increase in frequency and/or intensity of the condition.
- Signs, symptoms, or the clinical sequelae of a suspected overdose of a concurrent medication (overdose per se should not be reported as an AE/SAE).

Examples of an AE DO NOT include:

- Medical or surgical procedures (e.g. endoscopy, appendectomy); the condition that leads to the procedure is an AE.
- Situations where an untoward medical occurrence did not occur (e.g. social and/or convenience admission to a hospital, admission for routine examination).
- Anticipated day-to-day fluctuations of pre-existing disease(s) or condition(s) present or detected at the start of the study that do not worsen.

Example of events to be recorded in the medical history section of the CRF/eCRF:

- Pre-existing conditions or signs and/or symptoms present in a subject prior to the start of the study (i.e. prior to enrolment in an observational study).

6.1.2. Definition of a serious adverse event

A SAE is any AE that:

- a. Results in death,
- b. Is life-threatening,

NB: The term 'life-threatening' in the definition of 'serious' refers to an event in which the subject was at risk of death at the time of the event. It does not refer to an event, which hypothetically might have caused death, had it been more severe.

- c. Requires hospitalization or prolongation of existing hospitalization,

NB: In general, hospitalization signifies that the subject has been admitted at the hospital or emergency ward for observation and/or treatment that would not have been appropriate in the physician's office or in an out-patient setting.

Complications that occur during hospitalization are also considered adverse events. If a complication prolongs hospitalization or fulfills any other serious criteria, the event will also be considered serious. When in doubt as to whether 'hospitalization' occurred or was necessary, the adverse event should be considered serious.

Hospitalization for elective treatment of a pre-existing condition (known or diagnosed prior to informed consent signature) that did not worsen from baseline is NOT considered an SAE.

- d. Results in disability/incapacity, OR

NB: The term disability means a substantial disruption of a person's ability to conduct normal life functions. This definition is not intended to include experiences of relatively minor medical significance such as uncomplicated headache, nausea, vomiting, diarrhea, influenza like illness, and accidental trauma (e.g. sprained ankle) which may interfere or prevent everyday life functions but do not constitute a substantial disruption.

- e. Is a congenital anomaly/birth defect in the offspring of a study subject.

Medical or scientific judgment should be exercised in deciding whether reporting is appropriate in other situations, such as important medical events that may not be immediately life-threatening or result in death or hospitalization but may jeopardize the subject or may require medical or surgical intervention to prevent one of the other outcomes listed in the above definition. These should also be considered serious.

Examples of such events are invasive or malignant cancers, intensive treatment in an emergency room or at home for allergic bronchospasm, blood dyscrasias or convulsions that do not result in hospitalization.

6.1.3. Clinical laboratory parameters and other abnormal assessments qualifying as serious adverse events

Abnormal laboratory findings (e.g. clinical chemistry, hematology, urinalysis) or other abnormal assessments that are judged by the investigator to be clinically significant will be recorded as SAEs if they meet the definition of an SAE, as defined in Section 6.1.2.

Clinically significant abnormal laboratory findings or other abnormal assessments that are detected during the study or are present at baseline and significantly worsen following the start of the study will be reported as SAEs.

The investigator will exercise his or her medical and scientific judgment in deciding whether an abnormal laboratory finding or other abnormal assessment is clinically significant.

